4.2.14.2 Derivations

Not applicable.

4.2.14.3 Handling of Dropouts and Missing Data

If any of the criteria for SLEDAI-2K, BILAG or PGA cannot be evaluated at any visit up to Week 52, (e.g., due to missing values), the data for that criterion is imputed using LOCF and LLDAS derived based on the complete data. This applies only once. Missing data after LOCF will be imputed as non-responder. For example, if any of the Week 52 criteria data is missing and the data at Week 48 is not missing, the missing Week 52 criteria data will be imputed using the corresponding Week 48 data. Otherwise, the participant is defined as not achieving LLDAS at Week 52.

4.2.14.4 Primary Analysis of Exploratory Endpoints – LLDAS

The same CMH approach as described in Section 4.2.1.4 for the primary Exploratory is used to estimate the treatment difference between anifrolumab 300 mg and placebo as well as the response rates for all treatment groups for LLDAS response. Longitudinal

presentations of the results over time (i.e., for each post-baseline visit up to Week 52 during double blind treatment period) based on this analysis are created.

4.2.15 Exploratory Endpoint – Change in SDI

4.2.15.1 Definition

The endpoint used to evaluate the effect of anifrolumab versus placebo on irreversible damage in SLE participants is the difference in mean change in SDI global score from baseline to Week 52.

The SDI is defined for 12 organ systems as described in Section 4.1.6.1.

Furthermore, the number and percentage of participants with changes in damage will be explored at Week 52. A damage according to the SDI score is defined as an SDI global score ≥ 1 . Accordingly, no damage is defined as an SDI global score $= 0$. Post-baseline categories used for the presentation of change in damage will be ‘no change’, ‘+ 1 point’, ‘+ 2 points’, and ‘+ 3 or more points’.

4.2.15.2 Derivations

Not applicable.

4.2.15.3 Handling of Dropouts and Missing Data

Not applicable.

4.2.15.4 Primary Analysis of Exploratory Endpoint – Change in SDI

Observed values and changes from baseline in SDI global score will be presented by visit with descriptive statistics. This summary will be repeated by SDI global score at baseline (0 and ≥ 1).

Additionally, a shift table presenting damage according to the SDI score at baseline versus damage at Week 52 will be presented according to the categories given in Section 4.2.7.4.

4.2.16 Exploratory Endpoint – Lupus QoL

4.2.16.1 Definition

Lupus QoL

The difference between anifrolumab and placebo in the mean change from baseline in lupus QoL domain scores (physical health, pain, planning, intimate relationships, burden to others, emotional health, body image, and fatigue) will be assessed by visit up to Week 52.

The number of items in each domain and the item numbers that refer to that domain are tabulated in Table 3.

Table 3 Lupus QoL domains

Domain	Number of Items	Item Numbers
Physical Health	8	1 to 8
Pain	3	9 to 11
Planning	3	12 to 14
Intimate Relationships	2	15, 16
Burden to Others	3	17 to 19
Emotional Health	6	20 to 25
Body Image	5	26 to 30
Fatigue	4	31 to 34

Each item of the lupus QoL has a five-point Likert response scale (0=all the time, 1=most of the time, 2=a good bit of the time, 3=occasionally, and 4=never).

4.2.16.2 Derivations

Domain scores will be derived when at least 50% of the items are answered. The mean raw domain score is then calculated by totaling the item response scores of the answered items and dividing by the number of answered items. A non-applicable response is treated as unanswered. The mean raw domain score will be transformed to the domain scores (ranging from 0 as worst QoL to 100 as best QoL) as mean raw domain score divided by 4 and multiplied by 100.

4.2.16.3 Handling of Dropouts and Missing Data

Not applicable.

4.2.16.4 Primary Analysis of Exploratory Endpoint – Lupus QoL

Lupus quality of life (QoL) scale

Change from baseline in each of the lupus QoL domain scores (physical health, pain, planning, intimate relationships, burden to others, emotional health, body image, and fatigue) will be analyzed using repeated measures models with fixed effects for baseline value, treatment group, visit, and treatment*visit interaction stratification factors, and participant as random effect. Covariance parameters will be estimated using restricted Maximum Likelihood method and Kenward Rogers denominator degrees of freedom will be used for the tests of fixed effects. Thereby, an unstructured covariance matrix is used. In case of convergence issues, the following alternative structures is used for fitting (in that order): Heterogeneous Toeplitz, heterogeneous AR(1), Heterogeneous CS, Homogeneous CS. Longitudinal presentations of the results over time (i.e., for each post-baseline visit up to Week 52 during double blind treatment period) based on this analysis is created.

4.2.17 Exploratory Endpoint – EuroQol 5 dimensions (EQ-5D-5L)

4.2.17.1 Definition

The EQ-5D-5L is comprised of the following 5 dimensions: mobility, self-care, usual activities, pain/discomfort and anxiety/depression. The proportion of participants in each EQ-5D-5L health state (no problems, slight problems, moderate problems, severe problems and unable to/extreme problems), by dimension, as well as the VAS Score and single summary utility index, including changes from baseline, are explored over time.

EQ-5D-5L value sets are not available for all countries, therefore the UK value set is used for all participants in the study. By using the crosswalk link function and the individual responses to the EQ-5D-5L descriptive system, index values for the EQ-5D-5L is calculated (Van Hout, 2012).

4.2.17.2 Derivations

Not applicable.

4.2.17.3 Handling of Dropouts and Missing Data

Not applicable.

4.2.17.4 Not applicable. Primary Analysis of Exploratory Endpoint – EQ-5D-5L

The 5 dimensions of EQ-5D-5L (mobility, self-care, usual activities, pain/discomfort, and anxiety/depression) are summarized by timepoint as number and percentage of participants with the different health states.

Observed values and changes from baseline in VAS Score and single summary utility index, respectively, are presented longitudinally with descriptive statistics.

4.2.18 Exploratory Endpoint – Work productivity and Activity Impairment (WPAI)-Lupus

4.2.18.1 Definition

The Work Productivity and Activity Impairment (WPAI) is a validated, self-administered questionnaire consisting of 6 questions, assessing the impact of disease on productivity. The WPAI yields 4 types of scores: absenteeism (work time missed), presenteeism (VAS [scored from 0 to 10] rating of impairment while working), work productivity loss (overall work impairment /absenteeism plus presenteeism), and activity impairment (VAS [scored from 0 to 10] rating of daily activities, other than work at a job) (Reilly et al, 1993).

4.2.18.2 Derivations

The following variables are derived and presented:

Number of participants employed = number of participants with yes in response to

Question 1 (Q1)

Percentage of all participants employed

Number of work hours missed due to problems associated with lupus as responded in Q2

Absenteeism due to lupus (%) = $[Q2 / (Q2+Q4)] \times 100$

Presenteeism due to lupus (%) = $[Q5 / 10] \times 100$

Work Productivity Loss (%) = $(Q2 / (Q2+Q4) + [(1 - Q2 / (Q2+Q4)) \times (Q5/10)]) \times 100$

Activity impairment (%) = $[Q6 / 10] \times 100$

4.2.18.3 Handling of Dropouts and Missing Data

Not applicable.

4.2.18.4 Primary Analysis of Exploratory Endpoint – WPAI-Lupus

At each scheduled visit, the number and percentage of participants employed are presented. Observed values and changes from baseline in hours missed due to lupus and in WPAI scores (absenteeism, presenteeism, work productivity loss and activity impairment) are presented longitudinally with descriptive statistics.

4.2.19 Exploratory Endpoint – Medical Resource Use Questionnaire

4.2.19.1 Definition

The following variables are explored:

- Number of participants with health care visits
Of participants with health care visits
 - Number of specialist visits
 - Number of primary care visits
- Number of participants with emergency department visits
Of participants with emergency department visits:
 - Number of emergency department visits
 - Of emergency department visits:
 - Visit related to an increase in lupus related activity
 - Cause of emergency department visit
- Number of participants with hospital visits
Of participants with hospital visits:

- Number of hospital visits
- Of hospital visits:
 - Visit related to an increase in lupus related activity
 - Cause of hospitalization
- Length of hospital stay
- Total number of days in intensive care unit (ICU)

For all these variables, all available data between first administration of IP and Week 52 will be summed up.

4.2.19.2 Derivations

Not applicable.

4.2.19.3 Handling of Dropouts and Missing Data

Not applicable.

4.2.19.4 Primary Analysis of Exploratory Endpoint – Medical Resource Use Questionnaire

The medical resource uses are summarized by treatment. Results of “visit related to an increase in lupus related activity” and “cause of visit/ hospitalization” are presented as number and percentage of respective visits.

4.3 Pharmacodynamic Endpoint

See Section 4.2.9.

4.4 Pharmacokinetics

See Section 4.2.7.

4.5 Immunogenicity

See Section 4.2.8.

4.6 Safety Analyses

The following safety data are collected: vital signs, physical examination, 12-lead ECGs, clinical laboratory tests (including haematology, clinical chemistry, urinalysis and lipid profile), C-SSRS, Cushingoid features and AEs (including AEs of specific interest [AESIs]).

Safety analyses are performed using the safety analysis set. Unless otherwise specified, safety data are presented using descriptive statistics during the treatment and follow-up period.

Change from baseline to each post-treatment time point where scheduled assessments were made to calculate for relevant measurements.

If not stated otherwise, on-treatment values are defined as values with an assessment date after the first administration of IP and on or before the date of last administration of IP + 28 days.

4.6.1 Exposure

4.6.1.1 Definition and Derivations

The duration of exposure to the IP per subject is defined as the number of days between the start and the end dates of IP plus the dosing frequency interval:

Duration of exposure (days) = (Last dosing date + 28 days) – first dosing date + 1.

The total year of exposure is the sum of duration of exposure (days) of all subjects in the respective treatment group divided by 365.25 (days/year).

The total number of infusions are counted per participant. Furthermore, the number of participants with an infusion are assessed in 4-weekly categories (i.e., 4 Weeks, 8 Weeks, 12 Weeks, ..., 52 Weeks). An infusion will be counted if it was given in the corresponding time window. Missed infusions are not counted. Additionally, the number of participants with duration of exposure longer than each of the 4-weekly categories (i.e., ≥ 4 weeks, ≥ 8 weeks, ≥ 12 weeks, ..., ≥ 52 weeks) will be presented. As the duration of exposure takes into account the total exposure time from the last dose + 28 days (as defined above), any missed or delayed infusions will contribute to exposure time, but not to the number of infusions. For example, if a participant interrupted treatment and received no infusion at week 4, he/she will be counted as "No infusion" at week 4, but is counted as having "Exposure ≥ 8 weeks" if he/she received an infusion at any time after Week 4.

The time to discontinuation of IP is the same as the duration of exposure.

4.6.1.2 Presentation

Exposure is summarized by treatment group for the safety analysis set.

Summary statistics are provided for the duration of exposure. The number and percentage of participants treated ≥ 4 weeks, ≥ 8 weeks, and up to ≥ 52 weeks in 4-weekly intervals are provided. Furthermore, the total patient years of exposure is presented.

The number and percentage of participants with infusions are presented by total number of infusion (i.e., 1, 2, ..., 13) and by visit (i.e., Day 1, Week 4, Week 8, Week 12, ..., Week 48).

Furthermore, the time to discontinuation of IP is presented as Kaplan-Meier plot including the number of participants at risk (i.e., still on IP).

4.6.2 Adverse events

4.6.2.1 Definition and Derivations

Adverse events experienced by the participants will be collected throughout the entire study and will be coded using the latest version of MedDRA.

Adverse event data will be categorized according to their onset date into the following study periods:

- AEs occurring during screening:
An AE during screening is defined as an AE with a date of onset \geq date of first screening visit (S1) and $<$ date of the first dose of IP.
AEs occurring during screening will only be listed.
- AEs occurring during treatment period:
An AE during treatment period is defined as an AE with a date of onset \geq day of first dose of IP and \leq date of last dose of IP + 28 days.
- AEs occurring during treatment period and follow-up period:
An AE during treatment period and follow-up period is defined as an AE with a date of onset \geq day of first dose of IP and \leq date of last dose of IP + 84 days.
- AEs occurring after follow-up:
An AE after follow-up is defined as an AE with a date of onset $>$ date of last dose of IP + 84 days.
AEs occurring after follow-up will only be listed.

If an AE has a missing onset date, then unless the stop date of the AE indicates otherwise, this will be considered as an AE during treatment. Similarly, if an AE has a partial onset date, then unless the partial onset date or the stop date indicates otherwise, this will be considered an AE during treatment.

Adverse events of special interest are marked as such in the eCRF.

Adverse events with missing intensity will be assumed to be severe. Events with missing relationship to study medication per the investigator will be assumed to be related. If no information about seriousness is available, the AE will be considered serious.

An infusion-related reaction (as assessed by the investigator) is defined as an AE with a PT of “Infusion related reaction”.

An infection is defined as an AE within the SOC infections and infestations.

Opportunistic infections and serious non-opportunistic infections are identified by the investigator.

[figure not shown]
Hypersensitivity is defined as adverse events with MedDRA PT = “Hypersensitivity” and Lower level term (LLT) = “Hypersensitivity reaction”.

Herpes zoster is further classified according to the information given on the eCRF form “HERPZOS” as follows:

HZ Category	Cutaneous/Skin Involvement	Any organ involvement other than cutaneous/skin	Dermatome rule
Cutaneous Localized*	Yes	No	[≤ 3 contiguous unilateral dermatomes selected]
Cutaneous Disseminated	Yes	No	[> 3 contiguous unilateral dermatomes selected] or [non-contiguous dermatomes selected] or [dermatomes on left and right selected and/or bilateral selected]
Visceral Disseminated	Yes/No	Yes	[No rule]

* Cutaneous Localized is defined as below:

- CUTANEOUS/SKIN INVOLVEMENT = “YES”
- All affected dermatomes must be either “RIGHT” or “LEFT” not a mix of either or “BOTH”
- No more than 3 dermatomes are affected
- There is no other organ involvement
- There is an unbroken chain of affected dermatomes in the order that is presented in the image below.
 - The order is: V2, [(V1, V3) or (V3, V1) or (V1) or (V3)], C2, C3, C4, C5, C6, C7, C8, T1, T2, T3,... – T12, L1 – L5, S1 – S5

Adverse events during treatment are also presented by time intervals of the first onset of the event. For this analysis, repeated events with the same PT are not considered (i.e., if a participant has more than one event with the same PT, only the event with the earliest date of onset is used). For partial or missing dates, the rules as described above are used, i.e., the AE is considered as an AE during treatment unless the available information indicates otherwise and as occurring in the earliest possible time interval given the available (start and stop) date information. The following time intervals are defined:

- Day 1 to < Week 12:
AEs with date of onset \geq date of first administration of IP and < date of first administration of IP plus 84 days
- Week 12 to < Week 24:
AEs with date of onset \geq date of first administration of IP plus 84 days and < date of first administration of IP plus 168 days
- Week 24 to < Week 36:
AEs with date of onset \geq date of first administration of IP plus 168 days and < date of first administration of IP plus 252 days
- Week 36 to < Week 48:
AEs with date of onset \geq date of first administration of IP plus 252 days and < date of first administration of IP plus 336 days
- \geq Week 48:
AEs with date of onset \geq date of first administration of IP plus 336 days

Exposure-adjusted incident rate (EAIR) per 100 patient years is defined as

Sum of subjects with the event/[sum across subjects' time at risk for the event
/(365.25*100)]

Where time at risk is time to first event for subjects who experienced the event during the analysis period and time during the analysis period for subjects who do not experience the event.

The time to first onset of an event during a specified period is derived as date of first onset of the event during the specified period – date of first administration of study intervention + 1. Only AEs with an onset date during specified period will be counted. If a subject has no such event during the specified period, the time to first onset is censored at the end date of the period.

The time during the analysis period for subjects who do not experience the event will be calculated as end of period – start of period + 1 (e.g., date of last dose of IP + 28 days - day of first dose of IP + 1 day for summary of AEs during treatment period; date of last dose of IP + 84 days - day of first dose of IP + 1 day for summary of AEs during treatment and follow-up period). If a participant discontinued from the study during a period or had the last follow-up visit earlier than expected, the date of study discontinuation/end of study will be used as end of the respective period.

For the by timepoint analysis of anaphylaxis, hypersensitivity, and infusion related reactions, an AE at a visit is defined as an AE with a date of onset \geq day of administration of IP at the respective visit and \leq date of administration of IP at the following visit (or \leq date of last dose of IP + 28 days for the last visit with IP).

Other significant adverse events

During the evaluation of the AE data, a medically qualified expert will review the list of AEs that were not reported as serious AE (SAEs) or AEs leading to discontinuation.

Based on the expert's judgment, significant AEs of particular clinical importance may, after consultation with the AstraZeneca Global Patient Safety Physician, be considered other significant AEs and reported as such in the CSR.

Examples of these are marked hematological and other laboratory abnormalities, and certain events that led to intervention (other than those already classified as serious), dose reduction, or significant additional treatment.

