## **6.4 Recording of adverse events**

### **6.4.1 Time period for collection of adverse events**

Adverse Events and SAEs will be collected from time of signature of informed consent, throughout the treatment period and including the follow-up period until Follow-up Visit 2 (12 weeks post final dose). All SAEs, including ongoing or new SAEs occurring within the follow-up period 12 weeks after last dose of intravenous IMP, will be followed to resolution/stabilization regardless of the date of study completion. Events that reach a point of resolution/stabilization but with consequences are recorded as “resolved with sequelae.”

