### **6.4.3 Variables**

The following variables will be collected for each AE

- AE (verbatim)
- The date and time when the AE started and stopped

- Maximum intensity (mild, moderate, or severe)
- Whether the AE is serious or not
- Investigator causality rating against the Investigational medicinal product (yes or no)
- Action taken with regard to investigational medicinal product
- Outcome of AE

In addition, the following variables will be collected for SAEs:

- Date AE met criteria for serious AE
- Date Investigator became aware of serious AE
- AE is serious due to:
  - (a) Death
    - Date of death
    - Autopsy performed
    - Primary/secondary cause of death
  - (b) Life threatening
  - (c) Inpatient hospitalisation or prolongation of existing hospitalization
    - Date of hospitalization
    - Date of discharge
  - (d) Persistent or significant disability/incapacity
  - (e) Congenital abnormality or birth defect
  - (f) Important medical event
- Description of AE
- Investigator causality assessment to concomitant medications
- Investigator causality assessment to study procedures (yes or no)

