4.6.2.2 Presentation

If not stated otherwise, all summaries described below are presented separately for

- AEs during treatment period
- AEs during treatment and follow-up period.

An overall summary of participants with at least one AE in the following categories is presented.

- Any AE
- Any SAE with outcome = death
- Any SAE (including events with outcome = death)
- Any AE leading to discontinuation of IP
- Any AE related to IP
- Any AE of severe intensity
- Any AESI
 - Any AESI of serious non-opportunistic infections
 - Any AESI of opportunistic infections
 - Any AESI of herpes zoster
 - Any AESI of tuberculosis including latent tuberculosis
 - Any AESI of malignancy
 - Any AESI of major adverse cardiovascular events (MACEs)
- Any other significant AE.

If not stated otherwise, the number and percentage of participants with at least one AE (i.e., multiple occurrences of an AE in 1 participant will only be counted once) are summarized by MedDRA primary SOC and PT for the following AE categories. If not stated otherwise, the EAIR per 100 patient years will be presented for AEs during treatment. A 95% confidence interval for the difference between Anifrolumab and Placebo will also be constructed based on Mienttinen and Nurminen method (Liu et. al., 2006). EAIR will generally not be included in summaries presented for AEs during treatment and follow-up period.

- Any AE
- Any AE above reporting threshold of 2%

This summary is presented by PT.

- Any SAE with outcome = death

This summary is presented for AEs during treatment and follow-up period only. This summary will not include the EAIR per 100 patient years.

- Any SAE (including events with outcome = death)

- Any AE leading to discontinuation of IP

This summary is presented for all AEs during treatment period only.

- Any AE by relationship to IP (yes, no)

(Multiple occurrences of an AE in 1 participant will only be counted once as related if at least one AE is related and as not related if all occurrences are not related).

This summary is presented for AEs during treatment and follow-up period only and will not include the EAIR per 100 patient years.

- Any AE by maximum intensity (mild, moderate, severe)

(Multiple occurrences of an AE in 1 participant will only be counted once with the maximum intensity in this AE).

This summary is presented for AEs during treatment and follow-up period only and will not include the EAIR per 100 patient years.

- Any AESI

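### An AE record that starts before the first dose enters no AE summary table, even if it becomes serious, is fatal or leads to stopping study drug after dosing

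*SAP*

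**What the plan says.** Collection starts well before dosing. Protocol 6.4.1: "Adverse Events and SAEs will be collected from time of signature of informed consent". Screening lasts up to 35 days (SAP 3.3.1.2).

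Allocation to periods is in SAP 4.6.2.1: "Adverse event data will be categorized according to their onset date into the following study periods". The screening category is also defined by onset ("An AE during screening is defined as an AE with a date of onset" from the first screening visit up to, but not including, the first dose), and "AEs occurring during screening will only be listed". The two tabulated periods both begin on the day of first dose. One ends 28 days after the last dose, the other 84 days after it.

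SAP 4.6.2.2 then builds the tables on those two periods: "If not stated otherwise, all summaries described below are presented separately for" the treatment period and the treatment plus follow-up period. For fatal SAEs, "This summary is presented for AEs during treatment and follow-up period only". For AEs leading to discontinuation of study drug, "This summary is presented for all AEs during treatment period only".

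Protocol 6.4.3 has each AE carry a start and stop, one maximum intensity, an outcome and the action taken with study drug. For SAEs it adds a separate field, "Date AE met criteria for serious AE", and a date of death.

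**The concern.** The allocation rule looks only at when an event began, yet the data model allows the important part of an event to come later. A record that opens in screening and crosses the first dose keeps its pre-dose onset if the site updates that record. Nothing in SAP 4.6.2.1 then moves it into a tabulated period, whatever happens on study drug.

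Safety tables are read for single cases: a death, a serious infection, a withdrawal for an AE. Serious infection is a named important potential risk (protocol 1.3.1 and 1.3.3). A serious non-opportunistic infection is an AESI because it meets seriousness criteria (protocol 6.3.1), so an infection can become an AESI after dosing while its onset lies before it. The count of AE-related discontinuations in the AE tables could also differ from the count in the disposition table, with no rule to explain the difference.

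**Working it through.** The plan gives no figure to reproduce, so the check is to trace one record through the rules.

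**Test record (hypothetical):** mild AE, onset Day -3, first meets a seriousness criterion on Day 10, and study drug is then stopped. The site updates the open record.

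| Step | Rule | Result |
|---|---|---|
| 1. Period | SAP 4.6.2.1: treatment period and treatment plus follow-up both need onset on or after first dose | Fails both; classed as screening |
| 2. Missing-date rule | SAP 4.6.2.1: missing or partial onset counts as on treatment unless dates indicate otherwise | Not triggered; the onset is known |
| 3. Overall, SAE, AESI tables | SAP 4.6.2.2: the two post-dose periods | Not counted |
| 4. Fatal SAE table | Treatment plus follow-up only | Not counted, had the event been fatal |
| 5. AE leading to discontinuation | Treatment period only | Not counted |
| 6. Exposure-adjusted rate, time to first onset | SAP 4.6.2.1: only onsets inside the period count; others are censored at period end | Participant treated as event-free for the whole period |
| 7. Key subject information | SAP 4.6.2.2: treatment and follow-up period | Not included |
| 8. AE listing | SAP 4.6.2.1 | Included |
| 9. Disposition | SAP 4.1.1.2: reasons for stopping study drug and leaving the study, with no onset condition | Included |
| 10. Premature end of treatment in efficacy | SAP 4.2: taken from the DOSDISC form | Included |

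**Same episode, other recording habit:** if the site enters the Day 10 worsening as a new AE, its onset is Day 10. Step 1 passes, and the event appears in every table in steps 3, 5, 6 and 7 that applies to it. Two sites handling identical cases can therefore give different tables.

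**Size per case:** 260 participants randomised 1:1 gives 260/2 = 130 per arm. One participant left out of an incidence table changes that arm by 1/130 = 0.0077, or 0.77 percentage points.

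**How many cases:** the documents give no screening AE rate and no rate of later worsening. As an illustration only, assume 2 AEs per participant-year, the full 35 days of screening, and 1% to 5% of screening AEs later becoming serious, fatal or a reason to stop:

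- 260 × 2 × 35/365.25 = about 50 screening-onset AEs
- 1% of 50 = 0.5; 5% of 50 = 2.5

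Both rates are assumptions. The screening length is the maximum, since protocol 4.2 allows randomisation as soon as eligibility is confirmed. The 50 also include AEs that resolve before dosing. The range shows only that the count is likely to be very small.

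**The case against.** The strongest reply is that post-dose worsening may well be entered as a new AE. Protocol 6.1 lets an AE be a deterioration of something already present. Protocol 6.4.7 asks for deterioration from baseline in laboratory values, vital signs, ECGs and other safety assessments to be reported when it meets an SAE criterion or is the reason for stopping study drug, and for aggravated physical findings to be reported. Protocol 5.2.2 and 6.4.9 point the same way for changes since the screening examination and for worsening SLE. This narrows the point but does not remove it: none of these sections says that an AE still open at first dose must be closed and replaced by a new record when it worsens. The separate seriousness date does not settle it either way, because it also serves AEs that both start and become serious after dosing.

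A second reply is that eligibility and dosing checks make the obvious example rare. Infections needing oral anti-infectives within 2 weeks of Day 1 are excluded, as is mild COVID-19 within 6 weeks of first dosing (protocol 3.2). Eligibility is rechecked on Day 1 (3.3), and dosing is not to proceed during a clinically significant active infection (6.10.2, 7.2.2). That stands as a reason to expect few cases. It does not cover milder untreated infections or non-infectious AEs.

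Three stronger readings should be resisted. A reader might infer that such an event vanishes from all output; it does not, because the listing remains and a resulting discontinuation is in the disposition table. A reader might infer that a worsening screening AE always keeps its pre-dose onset; the documents do not say so. A reader might infer a known number of lost serious events; no such number can be taken from the documents.

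**Conclusion.** The point holds as a defect in the tabulation rule. An AE record with onset before first dose is excluded from every AE summary table by explicit wording, and no provision covers a change to serious, a fatal outcome or a permanent stop of study drug after dosing. Whether a given episode is lost depends on whether the site updates the old record or opens a new one, which is left unstated.

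The expected count is probably very small. The safety analysis is descriptive, and no efficacy result is affected. The consequence is confined to tables where one participant is worth about 0.77 percentage points of an arm and where single serious or fatal cases are read individually. The SAP is otherwise cautious about unknowns: missing seriousness is taken as serious, and a missing onset as on treatment unless the stop date indicates otherwise. Ignoring a recorded post-dose seriousness date sits oddly beside that. The change is worth making because it is cheap and closes a route by which a serious on-study event could be left out.

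**What to change.** Add to both tabulated period definitions in SAP 4.6.2.1: an AE with onset before first dose is also included if, on or after first dose and within the period, it first (a) met a seriousness criterion, (b) had a fatal outcome, or (c) led to permanent discontinuation of study drug. The date of that change is used as the event date, including for time to first onset and the exposure-adjusted rate.

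Sources for the dates:

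- (a) the date the AE met seriousness criteria and (b) the date of death, both in protocol 6.4.3;
- (c) the DOSDISC form, because protocol 6.4.3 lists the action taken with study drug without a date. The SAP should name the date it takes from that form.

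Add a rule against double counting: where the worsening was already entered as a separate post-dose AE, count the episode once. SAP 4.6.2.2 already counts a participant once per term, but the two records may be coded to different terms.

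Protocol 8.1 allows SAP amendments until unblinding. The cost is a few lines of SAP text, slightly more programming, and possibly a few more events in the tables.
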